The Effects of Parent-Child Activity Program on Physical Activity of Children With Cancer

March 31, 2024

1. Summary

Study Population: Children diagnosed with malignant tumors aged 6 to 14 years.

Outcome measures: ① Main outcome measures: physical activity behavior in children with cancer; ② secondary outcome indicators: height, weight, BMI, body fat, muscle, self-efficacy of physical activity, physical activity enjoyment, perceived social support in physical activity, and physical activity of parents.

Study Intervention: ① Control group: the children and their parents receive routine care and health education guidance, receive physical activity guidelines and suggestions for patients with malignant tumors provided by the researchers, and issue health knowledge education manual. In addition, the researchers and other members of the intervention team do not provide information about parent-child activities; ② Experimental group: the experimental group receives online and offline family-based parent-child physical activity intervention. It includes participating in offline group parent-child activities during hospitalization, including family competitive games and knowledge contests, etc., popularizing science of physical activity and parent-child sports activities to children and parents regularly after discharge, and pushing tweets, sports and practice videos related to physical activities and parent-child sports activities. Exercise were followed every 4 weeks and assessed for the previous session. The intervention protocol lasts 12 weeks and is followed up 3 months after the intervention is completed.

Sample size: with physical activity as the outcome indicator, the sample content was used to estimate the sample content calculation method, and the test level α was set to

0.05, and the control degree was 90%. According to the results of the literature review, 20.8621 subjects in the experimental group and the control group, considering 20% lost to follow up, so at least 27 subjects in the experimental group and the control group.

2. Introduction

2.1 Background

According to statistics, there are an estimated 429000 new cases of childhood malignancies each year^[1]. In recent years, childhood malignancy has ranked sixth in the total burden of world malignancy and ninth in the burden of childhood disease^[2]. At the same time, the incidence of malignant tumors in children and adolescents in China is also increasing, with a significant rate of 2.8% per year, which is the second leading cause of death in children^[3]. With the progress of modern medicine, the five-year survival rate of childhood malignancies in developed countries is as high as 80%^[1], The five-year survival rate of young children in China has also reached 72%^[2]. Therefore, childhood malignancies are a large group, and more professional medical personnel are needed to provide more and better quality treatment and care services. Although the current treatment program has significantly improved the treatment and survival of childhood malignancies in the past few decades, children still face a variety of health problems, especially in economically underdeveloped developing countries^[4]. These adverse effects may last for months to years, facing not only the physical and psychological effects of malignant tumors, but also various long-term adverse reactions such as growth and development disorders and secondary tumors

caused by treatment^[5]. Studies reported that 62.3% of patients with childhood malignancy had at least one chronic disease, such as type 2 diabetes, obesity and cardiovascular disease^[4]; 95% of patients with childhood malignancy develop chronic disease before the age of 45, and 80.5% develop disabling or life-threatening complications^[5]. Therefore, China launched the National Child Cancer Surveillance Program in 2019^[6]. To promote the health of patients, prevent and reduce the above health problems.

Physical activity (physical activity, PA) is any body activity caused by the skeletal muscle that leads to energy expenditure^[7]. Physical activity has been shown to have many benefits for the physical and mental health of children with malignantancies and can reduce the occurrence of these health problems. The American Cancer Society (Amarican Cancer Sociation, ACS) states that proper physical activity at all stages of cancer is good for health^[8]. However, the status of physical activity in children and patients with malignant tumors is worrying. Data from Western countries show that over 50% of children do not meet the recommended 60 minutes of moderate to high physical intensity per day^[9]; About 92.2% in Hong Kong, China did not meet the physical activity level recommended by the guidelines^[10]; 88.7% of children in mainland China are far from the daily exercise recommended by WHO^[11]. Physical inactivity not only increases the risk of various health problems, but is also an important cause of advanced cardiovascular disease and secondary tumors. Therefore, it is necessary to explore the methods that can effectively improve and maintain the

physical activity of children with cancer and reduce the occurrence of the above adverse reactions.

Scholars have developed various intervention programs for the physical inactivity of patients with childhood malignancy, Showing multiple health benefits, However, the effects of various intervention programs are not the same: the intervention programs supervised by professionals in the hospital has strict requirements on time, site and personnel; Physical activity plans at home due to lack of knowledge, inadequate supervision, Lead to low intervention compliance and no significant effect; With the development of mobile health and electronic health devices in recent years, Such as SMS, apps, real-time video calls, virtual reality technology, It offers broad prospects for remote intervention of physical activity in childhood malignancies^[12,13]. But home physical activity programs for children still require parental participation, guidance and supervision. The latest research shows that the parents to participate in the activity plan to improve compliance and intervention effect has positive influence: in professionals (such as medical staff or sports coach), under the guidance of parent-child activity plan participation and completion rate is as high as 90%, after intervention children with physical function, cardiopulmonary function, fatigue, quality of life, etc^[14]. However, such studies are still in the exploratory stage, the number of related studies is small, and the long-term health effects of the intervention are unknown, requiring more data to support them.

Cross-sectional studies show that physical activity in children with cancer is associated with multiple factors, including physical and psychological factors, family

support and participation, and peer support, among which children and family-related factors are the most important factors. Welk^[15] proposed the Youth Physical Activity Promotion Model which provides researchers with a comprehensive approach to promote adolescent physical activity by systematically understanding and improving the multiple factors that adolescent physical activity behavior. From the perspective of social ecology, the model constructed a framework including propensity factors (psychological attributes), facilitator factors (environment), reinforcing factors (social influence) and demographic variables. Validated by research^[16], The three factors covered by the model are able to effectively describe adolescent physical activity behavior, where physical activity self-efficacy and physical activity enjoyment in the tendency factors, and the influence of parents in the reinforcing factors are the most important aspects of the promotion of physical activity in adolescents. The Youth Physical Activity Promotion Model has been widely used in the physical activity research of school-aged children at home and abroad^[17], And reported good reliability and effectiveness, but has not been applied to construct physical activity intervention programs in children with tumors.

Therefore, this study is based on the Youth Physical Activity Promotion Model suitable for children child malignant tumor physical activity plan, aims to provide continuity care for children and their parents, by providing parents with physical activity knowledge and skills, increase the participation and interaction, increase social support for children and parents, improve the physical activity efficacy and physical activity enjoyment, so as to improve their physical activity behavior, promote

the life and health of children.

2.2 Risk / benefit evaluation

2.2.1 Potential risks

Due to the particularity of physical activity, children and parents may occur when participating in the activity, or may be due to exercise: ① bleeding; ② serious soft tissue injury; ③ fracture; ④ respiratory tract infection; ⑤ severe pain, intolerable; ⑥ fatigue, physical exhaustion, etc.

Countermeasures: The researchers have been strictly trained to accurately assess the health status of the subjects and timely treatment, and teach the parents common first aid skills, minimize the injury to the children and their parents, and evaluate and report according to the standard of adverse events.

2.2.2 Potential benefits

Studies have shown that effective and moderate physical activity has shown many benefits in both children with acute treatment and children who have finished treatment or are in long-term survival. Appropriate physical activity in children during the treatment of malignant tumors can effectively improve their physical and psychological conditions during the treatment period, such as the recovery of physical activity level^[18], And have increased muscle strength^[19], To reduce the cardiopulmonary injury caused by the treatment^[20], To relieve physical pain and fatigue^[19]Other discomfort symptoms and reduce anxiety and depression; proper physical activity can also effectively improve exercise ability and improve negative

mood^[21], And enhance the cardiopulmonary function^[22], And reduce the all-cause mortality rate^[23], enhance the quality of life^[21]。

3. Study objectives and outcomes

3.1 Purpose

This study is based on the Youth Physical Activity Promotion Model for children with cancer, aims to provide continuity care for children and their parents, by providing parents with physical activity knowledge and skills, increase the participation and interaction, increase social support for children and parents, improve their physical activity, and promote their life and health.

3.1.1 Main Purpose

Construct a parent-child activity intervention program suitable for children with cancer.

3.1.2 Secondary Purpose

(1) Describe the status quo of the physical activity, physical activity self-efficacy, physical activity enjoyment, family support and the physical activity of the parents of

the children with cancer, and analyze the influencing factors of the physical activity of the children with cancer;

(2) To explore the effect of parent-child activity intervention in children with cancer based on Youth Physical Activity Promotion Model on physical activity, physical activity self-efficacy, physical activity enjoyment, family support and parental physical activity of children with cancer.

3.1.3, exploratory purpose

To explore the feasibility of parent-child activity intervention in childhood malignancies based on Youth Physical Activity Promotion Models.

3.2 Study indicators

3.2.1 Main Indicators and Definitions

Physical activity (physical activity, PA): any body activity caused by skeletal muscle contraction higher than the basal metabolism^[25], Including occupational work, housework, leisure activities, sports, and physical exercise for fitness and health purposes^[26], Is divided into low (1.5~2.9MET), moderate (3.0~5.9MET) and intense (6.0 MET). The physical activity mentioned in this study refers to the regular, planned and organized physical activity to improve or maintain fitness, motor skills or health, the Chinese leisure activity questionnaire (Children's Leisure Activities Study Survey Chinese-version, CLASS-C) to measure the physical activity behavior of children with cancer, and the international physical activity questionnaire measures the physical activity behavior of parents.

3.2.2 Secondary indicators and Definitions

- (1) Physiological indicators: height, weight, body mass index (BMI), body fat of children. BMI is a simple index of height and weight, which is defined as the weight by kilogram divided by the square of the height by meter (kg/m^2). Body fat rate refers to the proportion of the fat weight in the human body in the overall body weight, also known as the body fat percentage, which reflects the content of fat in the human body.
- (2) Self-efficacy: Self-efficacy is based on Bandura's social cognition theory^[27], Refers to the individual's judgment of confidence in his / she performing a specific

behavior, and the individual's judgment of self-efficacy plays an important role in its decision whether to perform the behavior, degree of effort invested, and length of adherence. Physical activity self-efficacy is an individual's confidence in engaging and maintaining physical activity when faced a challenge^[28]. In this study, the simplified Chinese version of physical activity self-efficacy scale (shortened Chinese version physical activity self-efficacy scale, S-PASESC) was used to measure physical activity self-efficacy in pediatric patients with cancer.

(3) Enjoyment of physical activity (PA Enjoyment): enjoyment is a process of experiencing feelings such as happiness, interest and happiness, which is a subjective feeling^[29]. Physical activity enjoyment is a positive emotion for physical activity and represents a positive attitude towards physical activity, and this psychological experience can be driven by extrinsic support (e. g., social recognition) and internal feeling (e. g., sensory experience)^[30]. Enjoying is a key factor in motivating physical activity behavior and sustained participation, especially in the adolescent population^[31]; In turn, exercise was able to enhance participants' positive emotions. In this study, the brief physical activity enjoyment scale (short-form Physical Activity Enjoyment Scale, S-PACES) was used to measure the physical activity enjoyment in pediatric patients with cancer.

3.2.3 Safety Indicators

The number of unexpected events during the exercise intervention, including but not limited to fall, sprain, hypoglycemia, and infection during exercise.

4. study population

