4.1 Inclusion and exclusion criteria for young children with cancer

4.1.1 Inclusion Criteria

- (1) Aged 6~14 years old;
- (2) Diagnosed with cancer;
- (3) Undergoing cancer treatment;
- (4) Able to communicate in Chinese;

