5.3 Methods to reduce the bias

- (1) Adopt the research method of similar experiment, collect all the data of the experimental group, and then recruit the control group to collect the data to avoid the occurrence of contamination;
- (2) The intervention team members shall receive unified physical activity training and assessment before the intervention, jointly propose the possible situation during the implementation of the intervention, unify the interpretation method of the questionnaire items, and give unified language answers to the questions about the questionnaire;

(3) In the process of collecting the questionnaire, collect the questionnaire on the spot, evaluate and check the completion of the questionnaire, timely find and correct the missing contents, ensure the integrity and effectiveness of the questionnaire information, and timely input the data after collecting the questionnaire;

(4) When analyzing the data, check the integrity and validity of the data again, and make remedial plan for the incomplete questionnaire; establish a database, and two people jointly input and check the data to ensure the accuracy of data entry.

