6.1 Study Intervention

(1) Implement routine care in the control group

Children in the control group and their parents received routine care and health education guidance, as well as guidelines and suggestions on physical activity of patients with malignant tumors provided by the investigator, and issued health knowledge education manuals. In addition, the investigator and other members of the intervention team did not provide information on parent-child activities;

(Ii) The experimental group received the family-based parent-child physical activity intervention combining online and offline, specifically as follows:

(1) Information support:

I . Establish and use wechat groups

After obtaining the informed consent, the children with cancer and their parents were invited to join the wechat group, and the popular science of physical activity related knowledge was regularly pushed to the children and their parents every week. Children and their parents have any questions can be asked to the intervention team members in the group. In addition, every Monday, the researchers sent the physical activity clock in the group, inviting the children and parents to record after completing the physical activity.

II . Create and use a wechat official account

Create a wechat official account, and push tweets and video content related to physical

activity every Thursday, Saturday and Sunday morning.

III . Offline group parent-child activities

Inform the children with cancer and their parents to follow up every 4 weeks, and organize the follow-up children and their parents to participate in offline group parent-child activities.

(2) Personnel support:

I . Promote parental participation

- ① Improve parents 'physical activity knowledge, belief and ability: through wechat group, wechat public account and other ways, increase parents' understanding of children's physical activity knowledge, improve their belief and ability to supervise and participate in children's physical activity.
- ② Increase parent-child activities to promote parents' participation: push a variety of parent-child physical activities, such as two-person aerobics, two-person ball sports, and outdoor sports requiring family participation (such as mountain climbing), etc.
- ③ Organize family competitive games to promote parent-child interest.
- ④ Enhance parent-child communication, and jointly develop solutions to various problems.

II . Strengthen the role between families —— peer influence

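### Safety events are defined only for the exercise intervention and no matching collection is planned in controls, so any excess over background, especially of infection, cannot be estimated

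*Combined protocol and SAP*

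**What the plan says.** The safety indicator in section 3.2.3 is "The number of unexpected events during the exercise intervention, including but not limited to fall, sprain, hypoglycemia, and infection during exercise". It names no group, denominator, time window or rule for judging cause.

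Section 2.2.1 introduces its risks as ones that "children and parents may occur when participating in the activity, or may be due to exercise". It lists bleeding, soft tissue injury and fracture, followed by "④ respiratory tract infection; ⑤ severe pain, intolerable; ⑥ fatigue, physical exhaustion, etc". Its countermeasures have trained researchers assess subjects' health and "evaluate and report according to the standard of adverse events", but the standard, the groups covered and the period are not stated.

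In section 6.1 the control group has routine care and an education manual, "as well as guidelines and suggestions on physical activity of patients with malignant tumors provided by the investigator", while "the investigator and other members of the intervention team did not provide information on parent-child activities". Section 4.1.1 requires every child to be "Undergoing cancer treatment". Section 5.3 says the team will "collect all the data of the experimental group, and then recruit the control group to collect the data".

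Section 7 lists what is collected at T0 to T4: questionnaires, scales and physical measures. Adverse events are not on the list for either group. Section 5.4.2 describes no analysis of safety data.

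**The concern.** Infection, bleeding and fatigue can be expected in some children on cancer treatment whether or not they join an activity programme. A count tied to the programme therefore mixes background illness with any programme effect, or excludes illness whose link to the programme is delayed, depending on how the window is read. Infection is the hardest case. Its onset cannot be tied to a particular session, yet section 6.1 brings families together for offline group activities at the four-weekly follow-ups.

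Reporting may also differ between the groups. Experimental families have a WeChat group, a weekly activity record and monthly face-to-face interviews (sections 6.1 and 6.2). If events are picked up informally, they are more likely to surface there. Controls are also given activity advice, so their events are relevant in their own right.

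At stake is whether the final report can say anything about events beyond a list from one group.

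**Working it through.** The plan states no safety rate, safety power or safety denominator, so there is no safety figure to reproduce. The only usable input is the target per group in section 5.4.1: 21/0.8 = 26.25, rounded up to 27. All event rates below are assumptions.

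1. **Does any section supply a control count?** Section 3.2.3 ties the count to an intervention that controls do not receive (6.1). Section 2.2.1 promises adverse-event evaluation but places it under the risks of the activity. Section 7 has no event item and section 5.4.2 has no comparison of events. No section plans a control count.

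2. **What does the window mean?** There are two readings. If it means activity sessions, most background infections fall outside the count, and so do infections that appear days after a group session. If it means the 12-week programme, later-appearing infections within those weeks are counted, together with background infections. A matching control window could be defined under the second reading, but the documents do not define one. Neither reading covers the three months between T3 and T4.

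3. **Size of the background under the 12-week reading.** Expected children with an infection and no programme effect = 27 × rate. At 10% this is 2.7 and at 40% it is 10.8. For an observed count x, the implied excess runs from x − 10.8 to x − 2.7. That is a spread of 8.1 children, or 8.1/27 = 30 percentage points, which the plan's own data cannot narrow.

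4. **What a control count would add.** With a common rate p and 27 per group, the approximate 95% half-width for the difference is 1.96 × √(2p(1 − p)/27):
   - p = 10%: 16.0 points
   - p = 20%: 21.3 points
   - p = 30%: 24.4 points
   - p = 40%: 1.96 × √(0.48/27) = 26.1 points

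   Power at 27 per group (two-sided 0.05, normal approximation) is 17% for 10% against 20%, 36% for 20% against 40%, and 61% for 30% against 60%. Detecting 10% against 20% with 80% power would need 199 per group.

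5. **Zero events in one group.** The exact two-sided 95% upper limit is 1 − 0.025^(1/27) = 12.8%. With 21 evaluable children it is 1 − 0.025^(1/21) = 16.1%.

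**The case against.** The strongest reply is that this is a small exploratory study with no comparative safety aim in sections 3.1 or 5.1.1, and that section 2.2.1 already promises evaluation and reporting of adverse events. No section forbids recording control events, and the list in 3.2.3 is open-ended. Even identical counting would give a comparison confounded by calendar time, because controls are recruited after the experimental group, and it would detect only very large differences.

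Much of this stands. It limits the comparison to a descriptive one and makes the point an improvement to the plan, not a flaw in the activity analysis. It does not remove the gap: the promise in 2.2.1 sets up no control collection, and a rough comparator with an interval is more informative than none.

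A reader might infer three stronger things that the documents do not support:

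- **No event could be attributed to the programme.** A fall or sprain in a session can be linked to it case by case without a control rate.
- **The plan both misses post-session events and absorbs background illness.** These follow from different readings of the same ambiguous phrase. Each is a risk under its own reading, and they should not be added together.
- **The 12.8% limit measures the harm of having no comparator.** It reflects 27 children in one group and would be the same with a control count.

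**Conclusion.** The point holds in a limited form. Section 3.2.3 defines safety events only in relation to the exercise intervention, its window is ambiguous, and no section plans matching collection or comparison in controls. An excess over background therefore cannot be estimated, and this matters most for infection.

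Under the 12-week reading, and if background infection lies between 10% and 40%, the unresolved range is about 8 children in 27. The documents give no rate, so that size rests wholly on the assumption. The absence of planned control collection does not. Adding it would leave an uncertainty of roughly 16 to 26 points either side of the difference, before any allowance for dropout or for the confounding that comes with sequential, non-randomised groups.

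**What to change.** Redefine the indicator in section 3.2.3 as any adverse event since the last visit. Use the lists in 2.2.1 and 3.2.3 as prompts and add an open field for anything else, so that unlisted events are not lost. For each event record whether it occurred during or after activity and its judged relation to activity.

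Add the form to section 7 for both groups at T1, T2, T3 and T4, with the same wording and the same way of asking. It has to be in place from the first experimental child, because that group is completed before controls are recruited and later recall would not be comparable.

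Add to section 5.4.2: the number and proportion of children with at least one event, by group, with the difference and its exact 95% confidence interval. Give infection separately. Label the comparison descriptive, and state that the groups are sequential, non-randomised and about 27 each.

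The change needs no extra visits and leaves treatment, eligibility and sample size as they are. It costs slightly longer visits, some data entry, and recall error, which will be greatest over the three months before T4.
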